Research Code

Radiographic and Clinical Evaluation of Three-Dimensional Delta Plate in Internal Fixation of Mandibular Sub-condylar Fractures.

(Longitudinal Study)

Research Protocol

Submitted to the Department of Oral and Maxillofacial Surgery

Faculty of Dentistry, Ain Shams University.

**In partial fulfillment of the requirements of Masters' degree in Oral
and Maxillofacial Surgery.**

By:

[name]

**B.D.S. Faculty of Dentistry Ain Shams University
2019**

Email: [contact]

Under the Supervision of:

[name].[name]

Professor of Oral and Maxillofacial Surgery
Faculty of Dentistry
Ain Shams University

[name] [name]

Lecturer of Oral and Maxillofacial Surgery
Faculty of Dentistry
Ain Shams University

[name] [name]

Fellow of Oral and Maxillofacial Surgery
Ahmed Maher Teaching Hospital

Year of protocol registration

2023

Table of Contents

Topic	Page
I. Abstract	4
II. Background	5
III. Research Question	8
IV. Aims (Objectives)	9
V. Hypothesis	10
VI. Ethical Considerations	11
VII. Study design	13
VIII. Materials and Methods	14
• Study setting	15
• Sample Size	16
• Study Procedures	17
IX. Statistical Analysis	18
X. Funding of the Study	19
XI. References	20
XII. Arabic summary	23

I. Abstract:

Management of Sub-condylar fractures has been debatable for years, some surgeons advocate closed management if the situation permits, to avoid the complications associated with open reduction and internal fixation (ORIF). Nowadays, there are meticulous approaches and novel osteosynthesis systems that facilitate its open management but many of these systems need more research work to evaluate its efficacy.

In this study we intend to examine the efficacy of 3D delta plates from the radiographic and clinical point of view. This Single arm study will include 14 cases of trauma having mandibular sub condylar fractures, in which open reduction and internal fixation are indicated. After selecting patients according to the inclusion criteria, all patients will undergo open reduction and rigid fixation. Fracture will be stabilized using 4 hole, 2.0 mm 3-D Delta titanium plates using pre-auricular or retromandibular incision.

Postoperative clinical examination will be carried out on day three, day seven, one month and after three months. Postoperative radiographic examination will be performed immediately postoperative by CT scan.

II. Background:

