Indications for ORIF include bilateral fractures(relative), severe dislocation (> 10 degrees), other facial fractures affecting the occlusion, foreign bodies, lateral displacement of the condyle, and condyle displacement into the middle cranial fossa(11), mandibular nerve paraesthesia(12). Condylar fractures can be reached through trans -facial or intraoral approaches (13,14) .Singh et al (15) published the largest blinded, randomized controlled trial comparing open techniques with closed management; they concluded that both treatment options carry promising outcomes. However, the surgically treated group showed better results in all objective and subjective functional outcomes except for occlusion.

The gold standard osteosynthesis system is the use of two miniplates fixation secured with four screws each (16). However, some drawbacks such as; difficult accessibility that elongates operation time especially in higher fractures the use of double miniplates is associated with risk of facial nerve injury and subsequent facial nerve palsy. Moreover, the little amount of bone that is always encountered at the proximal part of the fracture (17).

Recently, Osteosynthesis devices with various shapes and sizes as single L, Y plate, or 3-D plate are used for the management of condylar fractures. Manufacturers tend to develop such systems to gain outcomes similar to that of the conventional 2 mini-plate system regarding functional stability and rigidity with less cost, less complications and less effort(17).

Several studies were conducted on three-dimensional plating systems such as Rhomboid, Trapezoid and Delta shaped plates that yielded good outcomes (17–21). One study claimed that trapezoidal condylar plate is convenient for low sub condylar fractures because of its wide dimensions, On the other hand, delta plate is suitable for both high and low sub condylar fracture. ((22–24)

The aim of this study is to evaluate the versatility of three-dimensional delta plate in reduction and fixation of this type of fracture in adult patients presented with unilateral sub-condylar fractures for primary ORIF. The results will be analyzed by radiographic assessment of proper anatomical reduction and measurement of vertical ramus height. In addition to, clinical outcomes of pain with jaw movements and measurement of all mandibular movements range.

III. Research Question:

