What are the radiographic and clinical outcomes of using three-dimensional Delta plate for primary open reduction and internal fixation of unilateral subcondylar fractures in adult patients?

PICOTS Elements:	
Patient/Problem	Adult patients presenting with unilateral sub condylar fracture, with or without concomitant facial or mandibular fractures.
Intervention	Primary ORIF using three-dimensional delta plate
Comparator	-
Outcome	Pain, posterior facial height, anatomic reduction, mouth deviation.
Time	3 months follow up
Setting	Faculty of Dentistry-Ain Shams University

IV. Aim of the Study, Research Objectives and Clinical Relevance Aim:

The aim of the study is to assess the efficacy of the delta plate in fixation of sub condylar fractures by radiographic evaluation of anatomic reduction and vertical ramus height and clinical evaluation of pain with jaw movements and range of mandibular movements.

Outcomes:

Primary outcomes: 1-Anatomic Reduction
2-Posterior Facial Height

Secondary outcomes: 1-Pain
2-Mandibular Movements.

Clinical Relevance:

Delta plate provides functionally stable osteosynthesis. In addition to, less periosteal dissection, and easier reduction and fixation of small fragments combined with the advantages of a smaller plate size, less cost and adequate stiffness (19,23).

V. Hypothesis:

Delta plate doesn't provide an added advantage over the other Osteosynthesis methods of Sub condylar fixation.

VI. Ethical consideration

Open reduction and internal fixation of sub condylar fractures is accompanied with complications such as facial nerve injury, parotid gland fistula, permanent scar, infection, pain, edema, and difficulty in mastication following surgical procedure.

Risk of Facial injury can be decreased by choosing the appropriate incision and meticulous dissection of the tissues.

Parotid gland fistula is avoided by suturing of parotid capsule or by retroparotid-retromandibular approach whenever possible.

Permanent scar is best minimized by minimal tissue trauma, suturing in layers then the skin will be sutured by Prolene 6-0, Topical antibiotics and topical silicone gel will be prescribed.

Risk of Infection is reduced by post-operative antibiotic.

Post-operative analgesics and anti-inflammatory medications will be given to control pain and edema.

Mastication force is enhanced by physiotherapy.

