All patients will undergo clinical evaluation of pain, mandible deviation on opening and closing, measurement of mandibular movements.

All patients will undergo pre-operative anesthetic evaluation which includes medical and surgical history, physical examination, investigations, risk assessment, consent and pre-medication.

Surgical Procedure:

All patients will undergo open reduction and internal fixation under general anesthesia.

The Fracture will be exposed either extraorally (submandibular or retromandibular or endaural approaches). The incision will be chosen according to the level of the fracture.

Fracture will be reduced; occlusion will be re checked then it will be fixated by 2.0 mm 3D Delta mini plates and anchored by 4 screws of 7-9 mm length.

Immediate post-operative medications:

All patients will take painkillers, anti-inflammatory, antibiotics and steroids.

Follow up:

Radiographic outcomes: The following will be measured on CT:

1-The vertical ramus height will be done by comparing the two sides from the glenoid fossa to the inferior border of the ramus on CT.

2- Accuracy of anatomical reduction detected on coronal and axial sections.

Radiograph will be taken immediately post-operative.

Clinical outcomes:

1- Assessment of pain by Visual Analogue scale.

2- Mandibular movements by a ruler:

-Lateral mandibular movement by measuring the horizontal distance between upper central teeth midline to the lower central teeth midline.

-Protrusive mandibular movement by measuring the transvere distance between upper central teeth midline to the lower central teeth midline.

-Maximal mouth opening by measuring the vertical distance between upper central teeth midline to the lower central teeth midline.

Follow up notes will be taken on day three, day seven, one month and Three months postoperatively.

IX. Statistical Analysis:

Regarding the continuous date, the T dependent test will be used to assess the statistical data. Regarding the discrete data, Chi Square test will be used to assess the statistical data significance, using SPSS Software.

X. Funding of the Study:

The research study will be self-funded by the operator. No internal or external funding will be shared in this study.

XI. References:

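### Both primary outcomes are read on one immediate postoperative CT, so they show the reduction achieved at surgery, not whether the plate holds it, although the aim is worded as efficacy in fixation

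*Protocol*

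**What the plan says.** Section IV of the protocol sets the aim as to "assess the efficacy of the delta plate in fixation of sub condylar fractures by radiographic evaluation of anatomic reduction and vertical ramus height", and the same sentence continues "and clinical evaluation of pain with jaw movements and range of mandibular movements". The outcome list below it opens with "Primary outcomes: 1-Anatomic Reduction", followed by posterior facial height. Pain and mandibular movements are secondary. Neither the aim nor the list says when the primary outcomes are measured.

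The timing is given elsewhere. The Abstract states: "Postoperative radiographic examination will be performed immediately postoperative by CT scan". For the clinical side it states: "Postoperative clinical examination will be carried out on day three, day seven, one month and after three months". In section VIII, under Follow up, ramus height and accuracy of reduction are described as CT measurements, and directly below them comes "Radiograph will be taken immediately post-operative".

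The last paragraph of the Background says that the study will "evaluate the versatility of three-dimensional delta plate in reduction and fixation of this type of fracture in adult patients". It then explains: "The results will be analyzed by radiographic assessment of proper anatomical reduction and measurement of vertical ramus height". That paragraph, too, adds the clinical measures of pain and jaw movement.

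**The concern.** Reduction and fixation are different things to evaluate. Reduction is how well the fragments were brought into place. Fixation also covers whether the plate keeps them there while the bone heals. A CT taken straight after the operation measures the first. It is taken too early to measure the second, because loss of position under the plate, if it happens, happens afterwards.

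The primary outcomes therefore do not reach the part of the aim that concerns holding. If the results are reported against the aim as worded, a good immediate reduction could be presented as primary evidence that the plate fixes the fracture well. The data bearing on the following three months come only from two secondary clinical measures. Pain and range of movement may respond to a loss of position, but they also depend on other things, so they are indirect evidence of it.

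**Working it through.** No sample size or test statistic is involved. The check is to set each outcome against its measurement times.

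**Assumption.** Section IV uses the term posterior facial height; the Follow up section measures vertical ramus height. I take these as the same outcome, since no other height measurement is described.

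| Outcome (section IV) | Rank | How measured | Before surgery | Immediately after | Days 3 and 7, months 1 and 3 |
|---|---|---|---|---|---|
| Anatomic reduction | Primary | CT | CT records displacement | CT | none |
| Posterior facial height | Primary | CT, side-to-side comparison | CT records ramus shortening | CT | none |
| Pain | Secondary | Visual analogue scale | yes | no separate reading stated | yes |
| Mandibular movements | Secondary | Ruler | yes | no separate reading stated | yes |

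The Follow up section also says that notes are taken at the four visits. This does not add imaging, because the Abstract assigns those visits to clinical examination and places the radiographic examination immediately after surgery.

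**What the primary data can estimate.** For patient *i*, let *H*(*t*) be the side-to-side difference in ramus height at time *t*, with *t* = pre, 0 (immediately after surgery) and 3 (three months).

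- Observed: *H*(pre) and *H*(0).
- Estimable: the mean of *H*(0), which is the symmetry achieved; and the mean of *H*(pre) − *H*(0), which is the correction obtained at surgery.
- Not estimable: the mean of *H*(3) − *H*(0), the change under the plate, because *H*(3) is never measured.

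Take two plates with the same *H*(0). Under the first, *H*(3) = *H*(0). Under the second, *H*(3) = *H*(0) + *δ*, a later shortening of any size *δ*. Both give the same primary data, whatever the value of *δ*. The same argument applies to anatomic reduction. The result does not depend on the number of patients, so neither the minimum of 10 nor the planned 14 changes it.

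**Against the aim.** The aim has four components. The two radiographic ones end at *t* = 0. The two that continue to three months are the secondary clinical ones.

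**The case against.** The strongest reply is that the protocol is consistent and delivers what it describes. The Abstract and the Follow up section agree on an immediate CT. The aim says how efficacy is to be judged, by the radiographic measures together with the clinical ones, and nowhere promises radiographic stability over time. Fixation may be shorthand for the whole procedure, since the research question in section III speaks of open reduction and internal fixation together. On that reading, an immediate CT with three months of clinical follow-up is a legitimate, if limited, design. No section announces a conclusion that goes beyond the data. A wording change would also leave the trial just as unable to see a plate that loosens later.

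Much of this stands. The imaging schedule is not contradictory, the choice of an immediate CT is defensible, and the clinical measures do belong to the aim. The wording change does not make later loss visible; it keeps the conclusion within what was measured. What remains is that the primary outcomes carry no stated time in section IV, and that the aim is worded around fixation when the primary measures stop at the reduction achieved. An analysis plan, if one exists, could word the conclusion carefully, but it could not supply readings that are never taken.

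Three stronger readings are tempting and are not supported:

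- A reader might infer that the three-month entry in the PICOTS table of section III contradicts the immediate imaging. It reads naturally as the length of the study, so it is not a contradiction.
- A reader might infer that the primary outcomes are invalid. They are valid for reduction and ramus height at the end of surgery.
- A reader might infer that the trial says nothing about fixation over time. The clinical measures are part of the stated aim, run to three months, and give some indirect information.

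**Conclusion.** The point holds as a limit on what may be concluded, not as an error in the imaging schedule. With one postoperative CT, taken immediately, and none at the four later visits, neither primary outcome can show that reduction or ramus height was maintained. The aim in section IV is worded more broadly than the primary outcomes can support.

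The size is minor to moderate. No estimate is biased for what it measures, and no numerical result changes; what changes is the claim that the primary results can carry. The conclusion rests on equating posterior facial height with vertical ramus height, and on taking fixation to include holding the fragments after surgery. If the investigators mean only the operation as performed, the clarification is smaller still, but it should be stated.

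**What to change.** Change the wording of the aim and outcome list in section IV, as follows:

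1. State that the two primary outcomes assess accuracy of reduction and ramus-height symmetry on the immediate postoperative CT.
2. Limit the primary conclusion to that.
3. State that any conclusion about fixation over three months rests on the secondary clinical outcomes, pain and mandibular movements, with no radiographic evidence of maintenance.

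This requires no added imaging, visits or patients, and leaves the outcomes and their ranking as they are. The cost is a narrower permitted conclusion: the trial could report how well the fracture was reduced with this plate, but not, as a primary finding, that the plate kept it reduced.

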The incidence of mandibular condylar fractures is estimated to be 17.5–52% making it the most seen mandibular fracture (1–4) sub condylar fractures are commonly encountered when the fracture is unilateral. However, in case of bilateral fracture pattern, the condylar heads are the ones that are fractured (5).

The reason for the high incidence of mandibular condyle fracture is attributable to the binding of the mandibular ramus with high stiffness and mandibular condyle head with low stiffness ((6) causative factors include physical trauma, road traffic accidents, violence, fall, sports, and gunshot wound. Internal causative factors include osteomyelitis, benign or malignant tumor, and muscular spasm during electric shock treatment (7).

The management of condylar fractures is highly controversial and includes observation, closed treatment, and open reduction. It depends on multiple factors such as the age of the patient, the co-existence of other mandibular or facial fractures, is it unilateral or bilateral, the level and displacement of the fracture, the stage of dentition and dental occlusion, the facilities in the area, patient's mental and physical conditions ((8).

Closed management of condylar fractures has lots of long-term complications like pain which is considered the most common complaint. In addition to esthetic problems like facial asymmetry due to shortening of ramus especially with unilateral fractures (9). Moreover, Temporomandibular diseases such as ankylosis, internal derangement of the temporomandibular joint (TMJ) and mouth deviation could happen. Nevertheless, Closed management is essential in some cases like simple patterns of fractures when occlusion is achievable, putting into consideration that patient's compliance, mental and physical status are crucial for successful treatment (8). Its main benefit (when indicated) is the avoidance of facial nerve injury, However, facial nerve injury risk is decreased as the operator's experience and skill increase(10) .

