Patients are allowed to withdraw from the trial whenever they want to. In this case, they will be surgically managed by conventional plating systems. All patients will be fully informed about the procedures. The risks and benefits will be thoroughly explained to them. No surgery will be performed without written consent.

All personal information and data of the patients will be preserved, maintained and stored in a special filing system available in the department. It will not be exposed to anyone that is not included in the surgical team.

The research ethics committee, Faculty of Dentistry Ain Shams University, will review the research plan.

VII. Study Design:

Longitudinal study.

VIII. Materials and Methods:

14 patients having unilateral sub condylar fractures will undergo open reduction and internal fixation by a single 4-hole miniplate 3D Delta plate. The dimensions of this plate are 1.0 mm thick, 20mm long, 5mm wide at top and 14 mm wide at the base. At the top of the plate is an arm with two longitudinally arranged holes, two more holes form the 2 corners of the base of the plate.

Study Setting:

Department of oral and maxillofacial surgery in the Faculty of Dentistry, Ain Shams University.

Sample Size Calculation:

The sample size was estimated based on research published by Manoj et al. study (2015) regarding fracture fixation by trapezoidal 3D plate in India, by fixing alpha at 0.05 (5%) and beta at 0.05(5%), the minimal sample size is 10 patients to be included. To avoid drop out the sample was increased to 14 patients(25).

Eligibility criteria

Inclusion Criteria:

- 1-Patients at or over 18 years.
- 2-Unilateral sub condylar fractures.

Exclusion Criteria:

- 1- Bilateral sub condylar fractures
- 2-Pediatric patients.
- 3-Intracapsular fractures
- 4-Patients with Uncontrolled systematic conditions.

Justification for Exclusions:

- Most clinical and radiographic assessments of bilateral sub condylar fractures are dissimilar to that of unilateral ones.
- The management of pediatric patients is totally different from that of adults.
- Intracapsular fractures is best treated by endoscopic approach or conservatively managed
- Patients with Uncontrolled systematic conditions are unfit for surgery.

Pre-operative Assessment:

All patients will undergo radiographic assessment with Computed Tomography to assess the level of the fracture, degree and direction of displacement and shortening of ramus height by comparing the two sides.

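### Lateral movement is read as the gap between the dental midlines with no zero in occlusion, so any resting offset that surgery corrects would enter the pre/post change

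*Protocol*

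**What the plan says.** The item is headed "2- Mandibular movements by a ruler" and gives this rule for lateral movement: "Lateral mandibular movement by measuring the horizontal distance between upper central teeth midline to the lower central teeth midline". It does not mention a starting reading in occlusion, the direction of the excursion, or the fractured side. No other section supplies them.

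The surrounding text bears on how the reading will be used:

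- Eligibility is limited to "2-Unilateral sub condylar fractures". The PICOTS table in section III allows concomitant facial or mandibular fractures.
- Pre-operative Assessment has CT determine displacement and ramus shortening by comparing sides. It also states: "All patients will undergo clinical evaluation of pain, mandible deviation on opening and closing, measurement of mandibular movements".
- After surgery: "Follow up notes will be taken on day three, day seven, one month and Three months postoperatively".
- For continuous data, section IX says "the T dependent test will be used to assess the statistical data". It does not name the visits to be paired.
- Section IV ranks mandibular movements as the second of two secondary outcomes.

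**The concern.** A distance between two midlines measures movement only if it starts from zero. If the lower midline already sits to one side with the teeth together, the ruler adds that offset to an excursion toward that side and subtracts it from an excursion the other way.

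A constant offset would drop out of a paired difference. Here, however, the operation reduces the fracture and rechecks the occlusion, so the offset may differ between the pre-operative and post-operative readings. The change in lateral range would then mix realignment of the jaw with recovery of movement.

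Because the rule does not tie the reading to a side, someone looking at the data later could not tell which way the error runs. An analysis plan cannot repair this: an offset and direction not written down at the visit cannot be recovered.

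**Working it through.** **Inputs.** From the protocol: the measurement rule, readings before surgery and at four post-operative times, a dependent t test, unilateral fractures, and a planned 14 patients. The protocol gives no midline offset, excursion or standard deviation, and its sample size is not tied to lateral movement. There is thus no stated figure to reproduce, and all millimetre values below are assumptions.

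**Step 1: what the ruler records.** Let E be the true excursion and d the resting offset.

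- Toward the shifted side: recorded = E + d
- Away from the shifted side: recorded = |E − d|

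**Step 2: error in the change.** Let the offset be d before surgery and 0 after, with d no larger than the pre-operative excursion.

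- Toward: E_post − (E_pre + d) = true change − d
- Away: E_post − (E_pre − d) = true change + d
- Mean of both: the errors −d and +d sum to zero

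**Step 3: numbers.** Assumed pre-operative excursions are 6 mm toward and 3 mm away, with 8 mm each way after surgery. True changes are 8 − 6 = +2 mm and 8 − 3 = +5 mm, with mean +3.5 mm.

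| d (mm) | Recorded change, toward (true +2) | Recorded change, away (true +5) | Recorded mean (true +3.5) |
|---|---|---|---|
| 1 | 8 − 7 = +1 | 8 − 2 = +6 | +3.5 |
| 2 | 8 − 8 = 0 | 8 − 1 = +7 | +3.5 |
| 3 | 8 − 9 = −1 | 8 − 0 = +8 | +3.5 |
| 4 | 8 − 10 = −2 | 8 − 1 = +7 | +2.5 |

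For d of 1 to 3 mm, each direction is wrong by exactly d and the mean is right. At d = 4 mm the offset exceeds the 3 mm excursion and the mean is wrong too.

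**Step 4: effect on the test.** Suppose there is no true change, one direction is analysed, and that direction bears the same relation to the shift in every patient. The paired t statistic is then noncentral with parameter √14 × (mean shift ÷ SD of differences). At a two-sided 5% level and n = 14:

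- SD 2 mm: false-positive rate 14%, 41% and 93% for a mean shift of 0.5, 1 and 2 mm
- Mean shift 1 mm: 64% at SD 1.5 mm, 21% at SD 3 mm

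If the direction read were instead always left or always right, the errors would differ in sign between patients. They would then tend to add spread rather than move the mean.

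**Step 5: after the fix.** Subtracting the occlusal offset at each visit gives (E + d) − d = E toward. Away, with position signed, it gives (E − d) + d = E. The offset term vanishes in both directions.

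**The case against.** The strongest reply is that the bias is conditional. A resting offset must exist, surgery must change it, the examiner must not subtract it informally, and the two directions must not simply be averaged. The pre/post contrast is also an inference from the pre-operative measurement and the dependent t test. Between post-operative visits a stable offset cancels. All of this stands, and so does the observation that every size shown is assumed.

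A reader might infer from the Background that midlines will often be displaced in these patients, because it mentions "facial asymmetry due to shortening of ramus especially with unilateral fractures". That does not follow. The sentence lists long-term complications of closed management and does not describe patients presenting for primary fixation. Nor does the pre-operative record of mandible deviation establish an offset at rest, since it concerns deviation during opening and closing. Plausibility rests instead on the unilateral injury, the CT assessment of displacement and ramus shortening, and the allowance for other mandibular fractures.

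A reader might also infer that the protocol fixes a single lateral value without a side. It is silent on this, and its references to the range of movements are compatible with recording both directions.

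What the reply does not remove is that the rule, followed as written, records position and leaves no zero against which to correct it.

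**Conclusion.** The point holds in conditional form. The definition equals lateral excursion only when the midlines coincide in occlusion, and nothing in the protocol ensures or checks that. If an offset d is present before surgery and corrected by it, the inferred pre/post change is in error by d mm, with opposite signs in the two directions. An assumed 1 to 3 mm offset gives an error of 1 to 3 mm per direction. Averaging both directions removes the error while d does not exceed the excursion, but the protocol does not specify this.

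The documents do not support a claim that the results will be biased, or that offsets are common. The false-positive rates show what could happen under the stated assumptions and are not predictions for this study. The reach is limited to one of three movement readings within a secondary outcome; anatomic reduction and posterior facial height are untouched. It is still worth correcting before data collection, because it is a bedside rule and the remedy is small.

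**What to change.** Replace the lateral-movement item with wording such as: *At each assessment the midline offset with the teeth in occlusion is recorded first, with its direction. Lateral excursion is the displacement of the lower midline from that position, recorded toward and away from the fractured side.*

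This costs one sentence in the protocol, one extra ruler reading per visit, and two lateral values to record. It needs no extra visit, staff or equipment. Whether the two directions are tested separately, averaged or only described can be left to the analysis plan. Separate tests would add comparisons in a study of 14 patients, and removing the bias does not require them.

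### Protrusive movement is defined by a side-to-side distance, so as written the forward range of the jaw is not measured (probably a wording slip; minor)

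*Protocol*

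**What the plan says.** Section IV of the protocol lists two secondary outcomes, pain and mandibular movements, and its aim refers to the range of those movements. The last paragraph of section II puts the scope more fully: "clinical outcomes of pain with jaw movements and measurement of all mandibular movements range".

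The operative definitions are in section VIII, under Follow up, Clinical outcomes, item 2, headed "2- Mandibular movements by a ruler". There are three:

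- Lateral movement: "Lateral mandibular movement by measuring the horizontal distance between upper central teeth midline to the lower central teeth midline".
- Protrusion: "Protrusive mandibular movement by measuring the transvere distance between upper central teeth midline to the lower central teeth midline".
- Mouth opening: "Maximal mouth opening by measuring the vertical distance between upper central teeth midline to the lower central teeth midline".

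Movements are also measured before surgery. The Pre-operative Assessment states: "All patients will undergo clinical evaluation of pain, mandible deviation on opening and closing, measurement of mandibular movements". The follow-up schedule is: "Follow up notes will be taken on day three, day seven, one month and Three months postoperatively". Section IX gives the analysis: "Regarding the continuous date, the T dependent test will be used to assess the statistical data".

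**The concern.** Protrusion is forward movement of the lower jaw. The direction word in its definition, misspelt in the protocol, can only sensibly be read as transverse, and in its ordinary sense that is side to side. The complaint is not the spelling: spelled correctly, the line still names the wrong axis.

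An examiner who followed it to the letter would record how far the lower midline sits to one side of the upper midline during protrusion. That is sideways drift, and it does not show how far the jaw came forward. The paired comparison in section IX would then test a change in drift under the label of protrusive range. A postoperative fall could mean a straighter movement, while a reader would take it as lost range. Readings taken along the wrong axis cannot be turned into forward range afterwards.

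**Working it through.** No figure in the protocol bears on this point, so there is nothing to reproduce. The check compares the three definitions, looks for a correction elsewhere, works through the geometry and counts the reach.

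**1. The three definitions side by side** (Follow up, Clinical outcomes, item 2)

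| Movement | Direction word | Landmarks |
|---|---|---|
| Lateral | horizontal | upper and lower dental midlines |
| Protrusive | transverse (misspelt) | the same |
| Mouth opening | vertical | the same |

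Stated as anteroposterior: 0 of 3.

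**2. Search for a correction.** Protrusion is defined nowhere else in the protocol. No anteroposterior, sagittal or overjet-type measure appears in it.

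**3. Does the landmark settle the direction?** No. A dental midline marks side-to-side position. It does not say whether a front-to-back distance would be taken from the incisal edge or the labial surface.

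**4. Geometry.** Let x be the side-to-side offset of the lower midline from the upper midline before the movement starts, s the sideways drift during protrusion, and d the forward travel.

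- Literal reading = |x + s|.
- For a straight protrusion s = 0, so the reading is |x| whatever the value of d. It is near zero when the midlines coincide at the start.
- Paired difference (post minus pre) = |x_post + s_post| − |x_pre + s_pre|.

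Forward travel d does not appear in that difference. If x is zero on both occasions, the difference is |s_post| − |s_pre|. A negative value then means less drift, and it carries no information about range.

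**5. Reach, counted from the Follow up section**

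- CT measures: ramus height and anatomical reduction = 2.
- Clinical measures: pain (1) + ruler measures (3) = 4.
- All follow-up measures: 2 + 4 = 6.
- Affected: 1 of 3 ruler measures, 1 of 4 clinical measures, 1 of 6 in all.
- Primary outcomes affected (anatomic reduction, posterior facial height): 0 of 2.

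These counts describe how far the wording reaches. They do not measure an effect.

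**The case against.** The strongest reply is that nobody would be misled. The line is labelled as protrusion and stands between lateral movement and mouth opening. Horizontal is already used for lateral movement, so a side-to-side reading would make two lines the same distance. Three different direction words suggest that three axes were meant, and the setting is a maxillofacial surgery department. This stands as evidence of intent, and it is why the point is minor. It does not supply a landmark, and nothing in the protocol corrects the word.

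A second reply is that transverse may mean lying in the transverse plane, which contains the forward direction. The text does not say so. That plane contains the side-to-side direction as well, so the line would still not fix which of the two is measured.

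A third is that a sideways reading could be a deliberate measure of deviation. The PICOTS table in section III lists mouth deviation as an outcome, and the Follow up section gives no separate measure of it. The Pre-operative Assessment, however, lists deviation on opening and closing apart from movements, and the line in question is labelled as protrusion. Neither fact alone is conclusive, but together they make a deliberate stand-in unlikely.

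The definition also cannot be left to an analysis plan. The protocol does not leave it open; it states a definition, and the stated direction is wrong.

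**Conclusion.** Wrong as written, minor severity. Taken literally, the protrusive line records a side-to-side offset and does not measure the forward range that sections II and IV promise. Taken loosely, its direction is not fixed. Either way the line needs correcting.

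The effect is confined to one of three ruler components of one secondary outcome. Pain, lateral movement, mouth opening, the two CT outcomes and the sample size are untouched.

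A reader might infer more than the protocol supports:

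- **That the trial's protrusion data will be invalid.** The protocol does not show whether examiners would follow the literal word, and the context suggests that a forward distance was meant. The conclusion concerns the text.
- **That the mandibular-movement outcome fails as a whole.** The lateral and opening definitions each name a direction that suits the movement.
- **That the error has a known size.** The protocol gives no figure from which one in millimetres could be derived.
- **That a full-contact reference reading or signed distances are required.** They go beyond the defect. The reason usually given for them, that the incisors may not start level, applies equally to the lateral and opening lines.

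The conclusion assumes that the misspelt word is transverse, and that the definitions given under Follow up also govern the pre-operative readings, for which no separate definition is stated.

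**What to change.** Replace the protrusive line with wording such as: *Protrusive mandibular movement: the anteroposterior distance, by ruler, between the upper and lower central incisors at maximum protrusion, taken at [incisal edge or labial surface].* Name one landmark, and use it at the pre-operative assessment and at all four follow-up visits so that the paired readings are like for like. The correction should be made before measurements are taken.

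The cost is one line of protocol text, with the same ruler, the same visits and no added reading.

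The sponsor may choose to add a reference reading with the teeth in full contact, but that has a cost: one more reading on each of 1 + 4 = 5 occasions, or 14 × 5 = 70 readings if all 14 patients attend throughout. That reference could also shift between the pre-operative and postoperative visits, because the protocol treats occlusion as something that facial fractures can affect (section II) and that is rechecked during surgery (Surgical Procedure). The reference reading is optional and is not part of this correction.
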